9.2 Sample Size/Accrual Rate

Planned sample size: 10-30 patients

As this is a phase 1 study, the sample size will be determined by the number of patients required to establish the MTD of IPdR given with capecitabine and RT. The statistical power of the correlative analyses with samples sizes of up to 30 patients is presented in Section 9.4.1.

Estimated patient accrual rate:

- Part IA: The accelerated titration design with single-patient cohorts will allow for an estimated patient accrual rate of 1 patient every 3 months.
- Part IB: Up to 3 patients at a time may be treated at a given dose level, allowing for an estimated patient accrual rate of 2-3 patients every 3 months.

PLANNED ENROLLMENT REPORT

Racial Categories	Ethnic Categories				Total
	Not Hispanic or Latino		Hispanic or Latino		
	Female	Male	Female	Male	
American Indian/ Alaska Native	0	0	0	0	0
Asian	1	1	0	0	2
Native Hawaiian or Other Pacific Islander	0	0	0	0	0
Black or African American	3	3	0	0	6
White	5	5	3	3	16
More Than One Race	2	2	1	1	6
Total	11	11	4	4	30

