9.4 Analysis of Secondary Endpoints

9.4.1 Correlative and exploratory biomarker analyses

Pre- to post-treatment changes in tissue biomarker levels measured on continuous and binary scales will be assessed using Wilcoxon signed rank or McNemar's tests, respectively (two-sided; $\alpha=0.05$). Associations between therapeutic response and baseline biomarker values or temporal changes in biomarkers will be explored using Fisher's exact tests or Wilcoxon rank sum tests. For the correlations between %IUDR-DNA incorporation and plasma PK, a two-sided Fisher's z-test with significance level of 0.05 and power of 80% will be used and the study will reject the null hypothesis (lack of correlation or $r_0=0$) if we observe a correlation with r ranging from 0.79 for $N=10$ subjects to 0.49 for $N=30$ subjects. For the correlation of %IUDR DNA incorporation in circulating granulocytes and peripheral blood counts and toxicities, assuming the target prevalence of grade 3/4 toxicity of 30%, the study will have a power of 80% with significance level of 0.05 on a two-sample means test to rule out the null hypothesis (equal means in groups with/ without grade 3/4 toxicity, $m_0=m_1$) if the observed mean %IUDR-DNA incorporation for patients with grade 3/4 toxicity is $m_1=3.3$ times the mean m_0 in the other group for $N=10$ enrolled subjects, and $m_1=2.1$ times the mean m_0 for $N=30$.

9.4.2 Determination of the pCR rate of IPdR + capecitabine + RT at the MTD

In rectal cancer, the absence of viable tumor cells in the resection specimen (primary tumor mass, surrounding tissue and lymph nodes, T0 N0 M0) at the time of surgery, termed pathologic complete response (pCR) (Ryan *et al.*, 2005; Martin *et al.*, 2012). pCR determination will be made by the pathologist at the treating institution.

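### Section 9.4.1 gives r = 0.79 (N=10) and 0.49 (N=30) as observed values that lead to rejection, but they are the true correlations detectable with 80% power; the named test rejects from about 0.63 and 0.36.

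*Combined protocol and SAP*

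**What the plan says.** Section 9.4.1 covers the correlative analyses. It begins "For the correlations between %IUDR-DNA incorporation and plasma PK, a two-sided Fisher's z-test" and goes on to give the level, the power and the decision: "z-test with significance level of 0.05 and power of 80% will be used and the study will reject the null hypothesis", the null being a correlation of zero, "if we observe a correlation with r ranging from 0.79 for $N=10$ subjects to 0.49 for $N=30$ subjects".

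Section 9.2 gives "Planned sample size: 10-30 patients" and points to these figures: "The statistical power of the correlative analyses with samples sizes of up to 30 patients is presented in Section 9.4.1". No passage states a separate rejection cut-off, and none calls 0.79 and 0.49 assumed true correlations.

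The next sentence of 9.4.1 compares mean incorporation between patients with and without grade 3/4 toxicity. It ties 80% power to ratios of 3.3 (N=10) and 2.1 (N=30) "if the observed mean %IUDR-DNA incorporation for patients with grade 3/4 toxicity is" that multiple of the mean in the other group.

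**The concern.** A test's rejection threshold applies to the sample correlation and depends on alpha and N. A detectable effect is a property of the population correlation and depends on power as well. The sentence joins the two: it attaches the rejection of the null to an observed correlation but prints numbers that belong to the true one.

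One sentence therefore holds two rejection rules for the same analysis, the 0.05 test and the printed r. They disagree for any observed r between 0.63 and 0.79 at N=10, or between 0.36 and 0.49 at N=30. In those bands the result is significant by the named test but below the value at which the plan says it will reject. The analysis serves secondary objectives 1.2.2 and 1.2.3 (incorporation in granulocytes and in tumor cells against IPdR PK). The risk is a real association reported as absent.

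**Working it through.** **Inputs, all from Sections 9.2 and 9.4.1.** Two-sided Fisher z-test; alpha 0.05; power 80%; null correlation 0; N from 10 to 30; printed r of 0.79 (N=10) and 0.49 (N=30). Normal quantiles: 1.960 for two-sided 0.05 and 0.842 for 80% power. On the Fisher scale the standard error is 1/√(N−3), that is 1/√7 and 1/√27.

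**Step 1. Reproduce the plan's figures.** The true correlation detectable with 80% power is tanh((1.960 + 0.842)/√(N−3)).
- N=10: tanh(2.802/√7) = 0.785
- N=30: tanh(2.802/√27) = 0.492

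These round to the printed 0.79 and 0.49. Alternatives fit less well: a one-sided 0.05 test gives 0.735 and 0.445, and a bias-corrected Fisher z gives 0.768 and 0.486. The printed values are therefore detectable true correlations.

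**Step 2. Where the named test rejects.** The critical observed |r| is tanh(1.960/√(N−3)).
- N=10: tanh(1.960/√7) = 0.630 (exact t-test: 0.632)
- N=30: tanh(1.960/√27) = 0.360 (exact t-test: 0.361)

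**Step 3. What follows if the printed values are used as cut-offs.** The simulated figures come from bivariate normal samples.

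| Quantity | N=10, cut-off 0.79 | N=30, cut-off 0.49 |
|---|---|---|
| Two-sided alpha, Fisher approximation | 0.0046 | 0.0053 |
| Two-sided alpha, exact t | 0.0065 | 0.0060 |
| Power when true r equals the cut-off, Fisher | 0.50 | 0.50 |
| Same, simulated | about 0.56 | 0.52 |
| True r needed for 80% power, tanh(atanh(cut-off) + 0.842/√(N−3)) | 0.883 | 0.603 |

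The Fisher power is 0.50 because, on that scale, the estimate is centered on its true value and falls above it half the time.

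**Step 4. What the p < 0.05 rule achieves.** At true correlations of 0.79 and 0.49 its power is 0.809 and 0.795 by the Fisher formula, and 0.85 and 0.81 by simulation. The stated 80% belongs to this rule.

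**Step 5. Results on which the two rules disagree.**
- r = 0.70, N=10: z = atanh(0.70) × √7 = 2.29, two-sided p = 0.022
- r = 0.45, N=30: z = atanh(0.45) × √27 = 2.52, two-sided p = 0.012

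Both reject at 0.05, and both lie below the printed values.

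**Side check on the mean-ratio sentence.** No SD is given, so this rests on assumptions: a two-sided equal-variance t-test and a 30% split (3 vs 7, and 9 vs 21). The standardized differences for 80% power are 2.209 and 1.156, and the ratio is 1 + d × SD/m0. With SD/m0 of 0.5, 1.0 and 1.5 it is 2.10, 3.21 and 4.31 at N=10, and 1.58, 2.16 and 2.73 at N=30. The printed 3.3 and 2.1 correspond to SD/m0 of (3.3−1)/2.209 = 1.04 and (2.1−1)/1.156 = 0.95. They are plausible if the SD is close to the mean, but the plan does not say so.

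**The case against.** The strongest reply is that nothing here is miscalculated. Both numbers are correct detectable correlations, Section 9.2 labels the content as power, and the sentence itself names the 0.05 test. It says the null is rejected if such an r is seen, not only if, and an observed 0.79 or 0.49 would indeed be rejected with p of about 0.005. The printed values also cover only the two ends of the range, so at N=20, say, an analyst would have to use the p-value anyway. The misreading would be conservative, and no dose, stopping or go/no-go rule uses these correlations.

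Much of this stands. The intent is clear, the numbers need no change, and a statistician who follows the named test would reach the right decision. But a sentence that gives the values at which a study will reject is read as a threshold, and as a threshold it contradicts the alpha and the power stated beside it. The label in Section 9.2 shows what was meant without correcting what 9.4.1 says.

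The mean-ratio sentence is a weaker case. It is already framed as a power statement and gives no rejection rule. Its only slip is to call the mean observed where the true mean is meant; the missing SD is an omission of detail and does not bear on the main point.

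**Conclusion.** The concern holds. The values 0.79 and 0.49 are correct as true correlations detectable with about 80% power and wrong as observed values marking rejection; the right cut-offs are about 0.63 and 0.36. Read as cut-offs, the printed values would cut two-sided alpha to roughly a tenth of its nominal size (0.005–0.007). Power at true correlations of 0.79 and 0.49 would be about 50–56%, and reaching 80% would take true correlations of about 0.88 and 0.60.

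These consequences arise only if someone applies the printed values literally. The Fisher figures use its normal approximation; the exact and simulated figures assume bivariate normal data, one pair of values per patient, and complete data on all 10 or 30 patients. The effect is confined to secondary correlative analyses: MTD determination, sample size and conduct are untouched. It should be corrected before analysis, but it does not threaten the trial's primary purpose.

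**What to change.** Reword the correlation sentence in Section 9.4.1 along these lines: *The null hypothesis of zero correlation will be rejected if the two-sided p-value is below 0.05 (observed |r| of at least about 0.63 for N=10 and 0.36 for N=30). The test has about 80% power if the true correlation is 0.79 (N=10) or 0.49 (N=30).* The p-value should be the rule and the two |r| values only illustrations, because the final N may lie anywhere between 10 and 30.

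In the mean-ratio sentence, refer to the true mean instead of the observed mean and, while the text is open, state the SD assumed for 3.3 and 2.1. No critical ratio should be printed there, since rejection depends on the observed SD and should follow the test's p-value.

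The cost is the wording of two sentences and one stated assumption. Sample size, dose escalation, sampling and conduct do not change.

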9.4.3 Determination of the Neoadjuvant Rectal Score

NAR is calculated based on the clinical T stage (cT), pathological T (pT) and pN stages as (Valentini *et al.*, 2011; George *et al.*, 2015):

$$\text{NAR} = [5\text{pN} - 3(\text{cT} - \text{pT}) + 12]^2 / 9.61$$

9.5 Analysis of Exploratory Endpoints

9.5.1 To explore the relationship between extent of exposure to RT and the incidence and severity of adverse events

9.5.2 To explore the interactions of capecitabine, IPdR and their metabolites

10. ADVERSE EVENTS: LIST AND REPORTING REQUIREMENTS

Adverse event (AE) monitoring and reporting is a routine part of every clinical trial. The following list of AEs (Section 10.1) and the characteristics of an observed AE (Sections 10.2 and 10.3) will determine whether the event requires expedited reporting via the CTEP Adverse Event Reporting System (CTEP-AERS) **in addition** to routine reporting.

10.1 Comprehensive Adverse Events and Potential Risks List (CAEPR)

10.1.1 CAEPR for IPdR (NSC 726188)

Comprehensive Adverse Events and Potential Risks list (CAEPR) For IPdR (NSC 726188)

The Comprehensive Adverse Events and Potential Risks list (CAEPR) provides a single list of reported and/or potential adverse events (AE) associated with an agent using a uniform presentation of events by body system. In addition to the comprehensive list, a subset, the Specific Protocol Exceptions to Expedited Reporting (SPEER), appears in a separate column and is identified with bold and italicized text. This subset of AEs (SPEER) is a list of events that are protocol specific exceptions to expedited reporting to NCI (except as noted below). Refer to the 'CTEP, NCI Guidelines: Adverse Event Reporting Requirements'
http://ctep.cancer.gov/protocolDevelopment/electronic_applications/docs/aeguidelines.pdf for further clarification.

NOTE: Report AEs on the SPEER **ONLY IF** they exceed the grade noted in parentheses next to the AE in the SPEER. If this CAEPR is part of a combination protocol using multiple investigational agents and has an AE listed on different SPEERs, use the lower of the grades to determine if expedited reporting is required.

Version 1.2, April 12, 2019¹

Adverse Events with Possible Relationship to IPdR (CTCAE 5.0 Term)	Specific Protocol Exceptions to Expedited Reporting (SPEER)
A Phase 1 safety study of single dose IPdR in 10 subjects resulted in no treatment-related adverse events. ^{2,3}	

¹This table will be updated as the toxicity profile of the agent is revised. Updates will be distributed to all Principal Investigators at the time of revision. The current version can be obtained by contacting [contact]. Your name, the name of the investigator, the protocol and the agent should be included in the e-mail.

²We expect the safety profile for oral IPdR to vary somewhat from the safety profile of iododeoxyuridine (IUDR), administered via continuous intravenous infusion in conjunction with localized radiation. Since oral IPdR is converted in the body to IUDR, the side effects of oral IPdR therefore may be similar to those adverse events observed in clinical trials of intravenous IUDR. The adverse events observed in IUDR clinical trials include: acute bowel obstruction, acute gastrointestinal hemorrhage, alanine aminotransferase increased, alkaline phosphatase

increased, anemia, aspartate aminotransferase, blood bilirubin increased, diarrhea, nausea, neutrophil count decreased, platelet count decreased, and weight loss.

³One early phase 1 single-dose safety clinical trial of IPdR (5-iodo-2-pyrimidinone-2'-deoxyribose) was conducted that treated 10 subjects resulting in no toxicities associated with IPdR. The safety profile may be revised during and after clinical trials are conducted using repeated dosing.

There is minimal (i.e., 10 subjects in a single-dose study) human data for IPdR to date, however no adverse events were noted in the study. The following toxicities have been observed during pre-clinical animal studies with IPdR:

Ferrets Only

Gastrointestinal disorders - Diarrhea; Nausea; Vomiting

HEPATOBILIARY DISORDERS - Increased liver weights

INVESTIGATIONS - Alkaline phosphatase increased

Metabolism and nutrition disorders - Anorexia

Nervous system disorders - Decreased motor activity

RENAL AND URINARY DISORDERS - Decreased kidney weights

REPRODUCTIVE SYSTEM AND BREAST DISORDERS - Decreased uterus weights

RESPIRATORY, THORACIC AND MEDIASTINAL DISORDERS - Bradypnea

Monkeys Only

Nervous system disorders - Lethargy

Rats Only

Blood and lymphatic system disorders - Anemia; Bone marrow (hyperplasia)

Investigations - Decrease alkaline phosphatase; Decreased hematocrit (Hct); Decrease in serum globulin; Decrease in total protein; Decreased RBC; Increased percentage of reticulocytes; Lobular atrophy in mandibular salivary glands; Lymphocyte count decreased

Ferrets, Rats, and Mice (events seen in all three species)

GASTROINTESTINAL DISORDERS - Acute bowel obstruction; Acute GI bleed

HEPATOBILIARY DISORDERS - Increased hepatic cytoplasmic vacuolization

Investigations - Alanine aminotransferase increased; Aspartate aminotransferase increased; Weight loss

Note: IPdR in combination with other agents could cause an exacerbation of any adverse event currently known to be caused by the other agent, or the combination may result in events never previously associated with either agent.

10.1.2 Adverse Event List for Capecitabine

- Gastrointestinal Disorders: Diarrhea, nausea, stomatitis, vomiting, abdominal pain, constipation, dyspepsia, elevated liver function tests

- Skin and Subcutaneous Tissue Disorders: Hand-foot syndrome, alopecia, rash, erythema, skin discoloration
- General Disorders: Fatigue, Pyrexia, asthenia, lethargy, anorexia
- Nervous System Disorders: Dizziness, headache, dysgeusia
- Blood and Lymphatic Disorders: Anemia, thrombocytopenia and neutropenia

10.2 Adverse Event Characteristics

- **CTCAE term (AE description) and grade:** The descriptions and grading scales found in the revised NCI Common Terminology Criteria for Adverse Events (CTCAE) version 5.0 will be utilized for AE reporting. All appropriate treatment areas should have access to a copy of the CTCAE version 5.0. A copy of the CTCAE version 5.0 can be downloaded from the CTEP website http://ctep.cancer.gov/protocolDevelopment/electronic_applications/ctc.htm.
- **For expedited reporting purposes only:**
 - AEs for the agent that are ***bold and italicized*** in the CAEPR (*i.e.*, those listed in the SPEER column, Section 10.1) should be reported through CTEP-AERS only if the grade is above the grade provided in the SPEER.
- **Attribution** of the AE:
 - Definite – The AE is *clearly related* to the study treatment.
 - Probable – The AE is *likely related* to the study treatment.
 - Possible – The AE *may be related* to the study treatment.
 - Unlikely – The AE is *doubtfully related* to the study treatment.
 - Unrelated – The AE is *clearly NOT related* to the study treatment.

10.3 Expedited Adverse Event Reporting

10.3.1 Rave-CTEP-AERS Integration

The Rave Cancer Therapy Evaluation Program Adverse Event Reporting System (CTEP-AERS) integration enables evaluation of Adverse Events (AEs) entered in Rave to determine whether they require expedited reporting and facilitates entry in CTEP-AERS for those AEs requiring expedited reporting. Sites must initiate all AEs for this study in Medidata Rave.

Include the following (highlighted) paragraphs about pre-treatment AEs only if the study requires reporting of pre-treatment AEs. Pre-existing medical conditions are not considered adverse events and therefore should not be reported on an Adverse Event form.

Pre-treatment AEs: AEs that occur after informed consent is signed and prior to start of treatment are collected in Medidata Rave using the Pre-treatment Adverse Event form.

Pre-existing medical conditions (formerly referred to as baseline AEs) identified during baseline assessment are not considered AEs and therefore should not be reported on the Pre-treatment Adverse Event form. If these pre-existing conditions worsen in severity, the investigator must reassess the event to determine if an expedited report is required. Whether or not an expedited report is required, the worsened event should be reported as a routine AE.

Treatment-emergent AEs: All AEs that occur after start of treatment are collected in Medidata Rave using the Adverse Event form, which is available for entry at each treatment course or reporting period and is used to collect AEs that start during the period or persist from the previous reporting period. AEs that occur 30 Days after the Last Administration of the Investigational Agent/Intervention are collected using the Late Adverse Event form.

Prior to sending AEs through the rules evaluation process, site staff should verify the following on the Adverse Event form in Rave:

- The reporting period (course/cycle) is correct, and
- AEs are recorded and complete (no missing fields) and the form is query-free.

The CRA reports AEs in Rave at the time the Investigator learns of the event. If the CRA modifies an AE, it must be re-submitted for rules evaluation.

Upon completion of AE entry in Medidata Rave, the CRA submits the AE for rules evaluation by completing the Expedited Reporting Evaluation form. Both NCI and protocol-specific reporting rules evaluate the AEs submitted for expedited reporting. A report is initiated in CTEP-AERS using information entered in Medidata Rave for AEs that meet reporting requirements. The CRA completes the report by accessing CTEP-AERS via a direct link on the Medidata Rave Expedited Reporting Evaluation form. Contact the CTSU Help Desk at [name] or by email at [contact] if you have any issues submitting an expedited report in CTEP-AERS.

In the rare occurrence that internet connectivity is lost, a 24-hour notification is to be made to CTEP by telephone at [contact]. Once internet connectivity is restored, the 24-hour notification that was phoned in must be entered immediately into CTEP-AERS

using the direct link from Medidata Rave.

Additional information about the CTEP-AERS integration is available on the CTSU members' website:

- Study specific documents: *Protocols > Documents > Protocol Related Documents > Adverse Event Reporting*, and
- Additional resources: *Resources > CTSU Operations Information > User Guides & Help Topics*.

NCI requirements for SAE reporting are available on the CTEP website:

- NCI Guidelines for Investigators: Adverse Event Reporting Requirements is available at https://ctep.cancer.gov/protocolDevelopment/electronic_applications/docs/aeguidelines.pdf.

10.3.2 Distribution of Adverse Event Reports

CTEP-AERS is programmed for automatic electronic distribution of reports to the following individuals: Principal Investigator and Adverse Event Coordinator(s) (if applicable) of the Corresponding Organization or Lead Organization, the local treating physician, and the Reporter and Submitter. CTEP-AERS provides a copy feature for other e-mail recipients.

10.3.3 Expedited Reporting Guidelines

Use the NCI protocol number and the protocol-specific patient ID assigned during trial registration on all reports.

Note: A death on study requires both routine and expedited reporting, regardless of causality as long as the death occurred less than 30 days after the last administration of the investigational agent. Attribution to treatment or other cause must be provided.

Death due to progressive disease should be reported as **Grade 5 “Disease progression”** in the system organ class (SOC) “General disorders and administration site conditions.” Evidence that the death was a manifestation of underlying disease (e.g., radiological changes suggesting tumor growth or progression: clinical deterioration associated with a disease process) should be submitted.

Phase 1 and Early Phase 2 Studies: Expedited Reporting Requirements for Adverse Events that Occur on Studies under an IND/IDE within 30 Days of the Last Administration of the Investigational Agent/Intervention ^{1,2}

FDA REPORTING REQUIREMENTS FOR SERIOUS ADVERSE EVENTS (21 CFR Part 312)

NOTE: Investigators **MUST** immediately report to the sponsor (NCI) **ANY** Serious Adverse Events, whether or not they are considered related to the investigational agent(s)/intervention (21 CFR 312.64)

An adverse event is considered serious if it results in **ANY** of the following outcomes:

- 1) Death
- 2) A life-threatening adverse event
- 3) An adverse event that results in inpatient hospitalization or prolongation of existing hospitalization for ≥ 24 hours
- 4) A persistent or significant incapacity or substantial disruption of the ability to conduct normal life functions
- 5) A congenital anomaly/birth defect.
- 6) Important Medical Events (IME) that may not result in death, be life threatening, or require hospitalization may be considered serious when, based upon medical judgment, they may jeopardize the patient or subject and may require medical or surgical intervention to prevent one of the outcomes listed in this definition. (FDA, 21 CFR 312.32; ICH E2A and ICH E6).

ALL SERIOUS adverse events that meet the above criteria **MUST** be immediately reported to the NCI via electronic submission within the timeframes detailed in the table below.

Hospitalization	Grade 1 and Grade 2 Timeframes	Grade 3-5 Timeframes
Resulting in Hospitalization ≥ 24 hrs	10 Calendar Days	24-Hour 5 Calendar Days
Not resulting in Hospitalization ≥ 24 hrs	Not required	

NOTE: Protocol specific exceptions to expedited reporting of serious adverse events are found in the Specific Protocol Exceptions to Expedited Reporting (SPEER) portion of the CAEPR.

Expedited AE reporting timelines are defined as:

- “24-Hour; 5 Calendar Days” - The AE must initially be submitted electronically within 24 hours of learning of the AE, followed by a complete expedited report within 5 calendar days of the initial 24-hour report.
- “10 Calendar Days” - A complete expedited report on the AE must be submitted electronically within 10 calendar days of learning of the AE.

¹Serious adverse events that occur more than 30 days after the last administration of investigational agent/intervention and have an attribution of possible, probable, or definite require reporting as follows:

Expedited 24-hour notification followed by complete report within 5 calendar days for:

- All Grade 3, 4, and Grade 5 AEs

Expedited 10 calendar day reports for:

- Grade 2 AEs resulting in hospitalization or prolongation of hospitalization

²For studies using PET or SPECT IND agents, the AE reporting period is limited to 10 radioactive half-lives, rounded UP to the nearest whole day, after the agent/intervention was last administered. Footnote “1” above applies after this reporting period.

Effective Date: May 5, 2011

